11. STATISTICAL METHODS

Statistical analysis will be performed by or under the authority of the sponsor. A general description of the statistical methods to be used to analyze the data collected in this study is outlined below. Specific details will be provided in the Statistical Analysis Plan.

11.1. Endpoints

The following endpoints will be analyzed:

- Incidence of serious adverse events in subjects exposed to Ad26.ZEBOV and/or MVA-BN-Filo in a Phase 1, 2 or 3 clinical study, up to 60 months after prime vaccination.
- Incidence of pregnancy with estimated conception within 28 days after vaccination with MVA-BN-Filo or within 3 months after vaccination with Ad26.ZEBOV.
- Incidence of pregnancy by pregnancy outcome.
- Incidence of live-born children from a pregnancy with estimated conception within 28 days after vaccination with MVA-BN-Filo or within 3 months after vaccination with Ad26.ZEBOV.
- Incidence of serious adverse events in children born from a pregnancy with estimated conception within 28 days after vaccination with MVA-BN-Filo or within 3 months after vaccination with Ad26.ZEBOV up to 60 months after birth.

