1. COHORT 1: VACCINATED SUBJECTS

Data collection schedule for subjects exposed to Ad26.ZEBOV and/or MVA-BN-Filo (or placebo) in a Phase 1, 2 or 3 clinical study:

	Visit 1 ^a	Contact 2 ^a	Subsequent Contacts ^a	End of Study ^a
	Baseline (Start of Data Collection) ^b	Month 6	Every 6 Months	After 60 Months of Follow-up ^c
Subject information				
Subject consent ^d	X			
Selection criteria	X			
Demographics ^e	X			
Ongoing subject review				
Serious adverse events ^{e,f}	X	X	X	X
Medication and vaccinations ^{e,g}	X	X	X	X
Study completion/withdrawal				
End-of-study form				$X^{\mathbf{h}}$

- a. Only the first visit is a study site visit (and may coincide with the last visit in the subject's original study); data collection at other time points will preferably occur through phone calls. If not possible by phone, a study site visit needs to be organized.
- b. Data collection can start when a signed informed consent form (ICF) is available for the current study. Preferably, this occurs at the last visit of the subject's original study. If this is not possible, baseline data will be collected when a signed ICF is available and data will be captured retrospectively from the subject's last visit in the original study up to the moment of enrollment in the current study.
- c. The subject should be followed for a total of 60 months after prime vaccination, including the duration in the subject's original study.
- d. Before the start of data collection in this study, all subjects and/or their legally-acceptable representative (where applicable) must sign an ICF for the current study indicating that he or she understands the purpose of and procedures required for the study and is willing to participate in the study.
- e. Relevant data will be copied from the analysis data set of the subject's original study. Any relevant new information should be added in the Case Report Form (CRF) of the current study.
- f. All serious adverse events are to be documented for a total of 60 months after prime vaccination (including the duration in the subject's original study).
- g. Any medication taken within a period of 30 days prior to the onset of a serious adverse event and up to the resolution of the serious adverse event.
- h. When an enrolled subject completes or withdraws from the study, or is lost to follow-up, the investigator will complete the end-of-study form for the individual subject and provide a specific date for the end-of-study observation(s).

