3. COHORT 3: OFFSPRING

Data collection schedule for children born to female subjects who became pregnant with estimated conception within 28 days after vaccination with MVA-BN-Filo (or placebo) or within 3 months after vaccination with Ad26.ZEBOV (or placebo) in a Phase 1, 2, or 3 clinical study:

	Visit 1 ^a	Visit 2 ^a	Subsequent Visits ^a	End of Study ^a
	Baseline (Start of Data Collection) ^b	Month 6	Every 6 Months	60 Months After Birth
Subject information				
Subject consent ^c	X			
Selection criteria	X			
Demographics	X			
Medical history ^d	X			
Ongoing subject review				
Serious adverse events ^e	X	X	X	X
Medication and vaccinations ^f	X	X	X	X
Growth measurements ^g	X	X	X	X
Study completion/withdrawal				
End-of-study form				X ^h

- a. Preferably, offspring from vaccinated female subjects will visit the study site for every study visit. If not possible, the child may be visited at home by study site staff or a qualified health care worker for data collection.
- b. Data collection can start when a signed ICF is available for the current study (at birth or as soon as possible after birth). If this is not possible, baseline data will be collected when a signed ICF is available and data will be captured retrospectively from birth up to the moment of enrollment in the current study.
- c. Before the start of data collection in this study, the subject's parent or legally-acceptable representative (where applicable) must sign an ICF for the current study indicating that he or she understands the purpose of and procedures required for the study and is willing to let their child participate in the study.
- d. Medical history of the child may include information on birth (preterm/full term), presence of birth defects, medical interventions beyond routine interventions at birth and relevant information from the mother's pregnancy follow-up, family history of growth (details on stature of parents and siblings).
- e. All serious adverse events are to be documented. Data collection should start with the time of birth and continue for 60 months.
- f. Any medication taken within a period of 30 days prior to the onset of a serious adverse event and up to the resolution of the serious adverse event.
- g. Height, weight, growth percentiles.

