3. STUDY DESIGN AND RATIONALE

3.1. Overview of Study Design

This is a multi-country, prospective, long-term clinical safety study designed to extend the total follow-up period of vaccinated subjects up to 60 months (including the duration in the subject's original study), to allow collection of serious adverse events and pregnancy outcomes (including

spontaneous/elective abortion, intrauterine death/stillbirth, information on delivery) following administration of Ad26.ZEBOV and/or MVA-BN-Filo for the prevention of Ebola virus disease among subjects who participated in a Phase 1, 2 or 3 clinical study. In addition, offspring from vaccinated female subjects who became pregnant with estimated conception within 28 days after vaccination with MVA-BN-Filo or within 3 months after vaccination with Ad26.ZEBOV in a Phase 1, 2 or 3 clinical study will be followed up to 60 months after birth. Up to approximately 3,000 subjects may potentially be enrolled in this study, based on the number of exposed subjects in the contributing Phase 1, 2 or 3 clinical studies.

Since validated assays are not available yet to assess immune responses in the ongoing Phase 2 and 3 studies, unblinding of these studies has been delayed. Therefore, subjects in the ongoing Phase 2 and 3 studies who reach the last study visit will be approached to consent for enrollment into the VAC52150 Vaccine Development Roll-over study for long-term safety surveillance (for a total of up to 60 months after the prime vaccination). After unblinding of their original study only subjects who received Ad26.ZEBOV and/or MVA-BN-Filo will remain in this VAC52150 Vaccine Development Roll-over study for long-term safety surveillance. After unblinding, subjects who received placebo and have already been enrolled into the VAC52150 Vaccine Development Roll-over study will be discontinued from further participation in this roll-over study. This also applies to pregnant subjects who received placebo (ie, subjects enrolled in Cohort 2) or offspring from vaccinated female subjects who received placebo (ie, subjects enrolled in Cohort 3).

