11.3. Analysis Sets

The Full Analysis set includes all subjects who were enrolled in this study and have at least one post-baseline visit, regardless of the occurrence of protocol violations.

The Restricted Analysis set includes all subjects who were enrolled in this study and have at least one post-baseline visit, have no major protocol deviations deemed to affect safety endpoints and have not been enrolled in any other clinical study.

The study endpoints will be analyzed based on the Full Analysis set as the primary analysis population. Additionally, the study endpoints may be analyzed based on the Restricted Analysis set as a secondary analysis population (sensitivity analysis).

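### Endpoint 1 counts SAEs from prime vaccination, but only subjects who survive to roll-over consent and a post-baseline visit are analysed, so early fatal SAEs cannot be counted

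*Protocol*

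**What the plan says.** Section 11.1 sets the first endpoint as SAE incidence in subjects exposed to either vaccine "in a Phase 1, 2 or 3 clinical study, up to 60 months after prime vaccination". The Cohort 1 Time and Events Schedule gives the matching collection window in footnote f: "All serious adverse events are to be documented for a total of 60 months after prime vaccination", with the original study's duration included. The early part of that window is filled in two ways:

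- For the original study itself: "Relevant data will be copied from the analysis data set of the subject's original study" (footnote e, attached to the SAE row).
- For any gap after it: "data will be captured retrospectively from the subject's last visit in the original study up to the moment of enrollment in the current study" (footnote b).

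Entry comes later than the start of the window. Section 5.1, criterion 2, requires a newly signed ICF, and Cohort 1 footnote a makes Visit 1 a site visit. Section 3.1 adds that "subjects in the ongoing Phase 2 and 3 studies who reach the last study visit will be approached to consent for enrollment". The Full Analysis set, which is primary, "includes all subjects who were enrolled in this study" provided they also have a post-baseline visit (Section 11.3). The first scheduled contact after baseline is at Month 6.

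Section 11.5 asks for two measures for each SAE: the percentage of subjects with at least one occurrence, and events per person-year. It does not say where person-time begins. Section 12.3.1 makes the cause of a death an SAE. Section 11.2 warns of observational bias, loss to follow-up and data not routinely collected, but does not mention survival to entry.

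For Cohort 3, footnote b says "data will be captured retrospectively from birth up to the moment of enrollment in the current study" when consent is not obtained at birth.

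**The concern.** The window opens at prime vaccination, but membership of the analysed group is settled months later by being alive, consenting and having a further visit. Every analysed subject brings a stretch of follow-up in which death was impossible by construction. Someone who died in that stretch contributes neither the event nor the time. This is immortal time from delayed entry.

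The error has one direction. Fatal SAEs are understated, and the unseen stretch is the one closest to vaccination. The study exists to document the long-term safety profile for benefit-risk purposes (Sections 2.1 and 2.2), so a favourable bias built into its first endpoint matters even though nothing is tested.

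The analysis-set rule adds to it. A subject who consents and dies before the first later contact drops out of the primary analysis, although that death falls within the study's own prospective follow-up.

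**Working it through.** The protocol states no rate or precision target, so there is no figure of its own to reproduce.

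**Inputs from the protocol:** a 60-month window from prime vaccination (11.1); up to about 3,000 subjects (11.2); first post-baseline contact at Month 6 (Cohort 1 schedule).

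**Assumptions, not in the protocol:** consent at month 6, 12 or 24 after prime; a constant fatal SAE rate λ of 1, 3 or 10 per 1,000 person-years; N = 3,000 analysed; no other loss; person-time counted from prime.

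**Formulas**, with e the time in years from prime to the point a subject must survive to:

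- Deaths counted: D = N(1 − exp(−λ(5 − e)))
- Person-years after e: P = D/λ
- Rate with the clock at prime: D/(N·e + P)
- Rate with the clock at entry: D/P = λ
- Deaths unseen before e: N(exp(λe) − 1)

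**Worked case, λ = 0.003, consent at month 12 (e = 1):**

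- D = 3,000 × (1 − exp(−0.012)) = 35.8
- P = 35.8/0.003 ≈ 11,928
- Rate = 35.8/(3,000 + 11,928) = 2.40 per 1,000, against a true 3.00; ratio 0.80
- Unseen deaths = 3,000 × (exp(0.003) − 1) = 9.0

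If survival to the Month 6 contact is also required (e = 1.5), 31.3 deaths are counted, 13.5 are unseen, and the rate reads 2.10 (ratio 0.70).

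| Assumed consent | Death-free person-years before consent | Rate read (true 3.00) | Ratio | Rate read with post-baseline rule | Ratio |
|---|---|---|---|---|---|
| Month 6 | 1,500 | 2.70 | 0.90 | 2.40 | 0.80 |
| Month 12 | 3,000 | 2.40 | 0.80 | 2.10 | 0.70 |
| Month 24 | 6,000 | 1.80 | 0.60 | 1.50 | 0.50 |

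The ratios hardly depend on λ: without the post-baseline rule they are 0.900, 0.800 and 0.600 at 1 per 1,000, and 0.898, 0.797 and 0.596 at 10 per 1,000. A simulation of 2,000,000 subjects at 3 per 1,000 agreed.

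**The percentage measure does not depend on the clock.** In the worked case 35.8/3,000 = 1.19% of analysed subjects have a fatal SAE. The source cohort would show (35.8 + 9.0)/3,009 = 1.49%. The ratio is again 0.80.

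**Moving the clock to consent is not enough if the post-baseline rule stays.** The first 6 months after consent then remain death-free. For a small hazard the ratio is about (60 − 18)/(60 − 12) = 42/48 = 0.88 for consent at month 12, 48/54 = 0.89 for month 6 and 30/36 = 0.83 for month 24.

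**All SAEs.** The protocol gives no share of SAEs that are fatal. Purely as an illustration, if 10% were fatal, the lost deaths would lower the event count by 0.10 × 0.20 = 2% (0.10 × 0.10 = 1% to 0.10 × 0.40 = 4%). This leaves out non-fatal SAEs in people who never entered.

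**The case against.** The strongest reply is that the protocol never puts pre-consent time in a denominator. Section 11.5 is silent on the clock, Section 11 leaves details to the statistical analysis plan, Section 9.2.2 ties SAE recording to the prospective period, and Section 11.2 speaks of prospective cohort data. A delayed-entry analysis would remove the bias in the rate. This stands in part: the size of the rate bias is conditional on the clock. But the window, the entry condition and the analysis set are fixed in the protocol. A consent-start clock would no longer estimate endpoint 1 as written, and it would leave the percentage measure conditional on survival.

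The reply also notes that deaths during the original studies belong to those studies' data, and that this study is meant to add follow-up beyond them (Section 1.3). That stands. A reader might infer that the deaths disappear from the development program; the protocol does not support this.

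Three other stronger readings go too far:

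- *Early leavers are excluded by rule.* Criterion 1.2 admits anyone exposed, and Section 9.1 allows later consent. The wording in Section 3.1 explains why still-blinded subjects are approached. It fits poorly with criterion 1.2 but is not an exclusion.
- *Children who die before consent cannot enter Cohort 3.* A parent or representative signs (footnote c), so their loss is likely, not certain.
- *Nearly all early deaths are lost because risk is concentrated after vaccination.* Nothing in the protocol indicates such a concentration.

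Finally, the study is descriptive, with no hypothesis. That removes any concern about error rates, but not about a biased estimate.

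**Conclusion.** The point holds for fatal SAEs. As written, endpoint 1 claims a 60-month incidence from prime vaccination that cannot include deaths before consent, and the primary analysis set also drops deaths before the first later contact. With the clock at prime vaccination, the fatal rate would be about 0.90, 0.80 or 0.60 of the truth, or 0.80, 0.70 or 0.50 with the post-baseline rule. These figures rest on assumed consent at month 6, 12 or 24, a constant hazard and no other loss. The protocol gives neither the consent timing nor a death rate.

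A reader might carry these ratios over to the whole SAE rate. That is not supported: enrolled subjects' earlier non-fatal SAEs are counted, so the overall effect is smaller, and the protocol does not allow it to be sized.

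**What to change.** - **Sections 11.1 and 11.5:** report SAE incidence and events per person-year with risk time starting at roll-over consent (delayed entry). Present events copied from the original study, or captured retrospectively before consent, in a separate table labelled as conditional on survival to enrollment. Do not pool that period into the fatal rate.
- **Section 11.3:** drop the post-baseline-visit condition from the Full Analysis set for SAE endpoints, so that deaths soon after consent count.
- **Cohort 3:** start person-time at consent in the same way.
- **Section 11.2:** name survival to entry as a limitation.
- **Reconcile** the last-visit wording in Section 3.1 with criterion 1.2, and the prospective-period wording in Section 9.2.2 with the 60-month window.
- **Optional:** after unblinding, show the original studies' SAE and death counts for all vaccinated subjects alongside.

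The cost is protocol and analysis-plan wording, with no new procedure for enrolled subjects. Pre-consent time leaves the headline rate. With consent at month 12, 20% of person-time goes, and the interval for a constant all-SAE rate widens by a factor of about 1/√0.8 = 1.12 (1/√0.9 = 1.05 at month 6, 1/√0.6 = 1.29 at month 24). The fatal rate loses no counted events, because none could occur in that time. The reported rate may look less favourable.

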2. COHORT 2: PREGNANCY OUTCOMES

Data collection schedule for female subjects who became pregnant with estimated conception within 28 days after vaccination with MVA-BN-Filo (or placebo) or within 3 months after vaccination with Ad26.ZEBOV (or placebo) in a Phase 1, 2, or 3 clinical study:

	Visit 1 ^a	End of Pregnancy Follow-up ^a	
	Baseline (Start of Data Collection) ^b	End of Pregnancy	
Subject information			
Subject consent ^c	X		
Selection criteria	X		
Demographics ^d	X		
Ongoing subject review			
Serious adverse events ^{d,e}	X	X	
Medication and vaccinations ^{d,f}	X	X	
Pregnancy follow-upg	X	X	
Study completion/withdrawal			
Transition to Cohort 1h		X¹	

- a. Only the first visit is a study site visit; data collection at the end of the pregnancy will preferably occur through a phone call. If not possible by phone, a study site visit needs to be organized.
- b. Data collection can start when a signed ICF is available for the current study. Preferably, this occurs at the last visit of the subject's original study. If this is not possible, baseline data will be collected when a signed ICF is available and data will be captured retrospectively from the subject's last visit in the original study up to the moment of enrollment in the current study.
- c. Before the start of data collection in this study, all subjects and/or their legally-acceptable representative (where applicable) must sign an ICF for the current study indicating that he or she understands the purpose of and procedures required for the study and is willing to participate in the study.
- d. Relevant data will be copied from the analysis data set of the subject's original study. Any relevant new information should be added in the CRF of the current study.
- e. All serious adverse events in subjects exposed to Ad26.ZEBOV (or placebo) and/or MVA-BN-Filo (or placebo) are to be documented. Data collection should start with study enrollment and continue until the end of the pregnancy.
- f. Any medication taken within a period of 30 days prior to the onset of a serious adverse event and up to the resolution of the serious adverse event.
- g. Information on obstetric history, maternal/paternal risk factors, pregnancy outcome (including spontaneous/elective abortion, intrauterine death/stillbirth, information on delivery).
- h. After the pregnancy, female subjects will continue to be followed up in Cohort 1. A live-born child will be followed up in Cohort 3.

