Each local authority will determine which cohorts will be opened for enrollment in their region. It is not mandatory to open all cohorts for enrollment. As a result, a local authority may restrict enrollment to 1 or 2 cohorts, rather than allowing enrollment in all cohorts.

After unblinding of their original study, subjects from Cohort 1 and 2 who received placebo or offspring (Cohort 3) from female subjects who received placebo will be discontinued from further participation in this roll-over study.

The study is considered completed with the last data collection time point for the last subject participating in the study. Further details of study completion and termination procedures are presented in Section 17.9.

Relevant Independent Ethics Committee (IEC)/Institutional Review Board (IRB) and Health Authority approvals will be secured prior to initiating the study.

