5.1. Inclusion Criteria

Each potential subject must satisfy all of the following criteria to be enrolled in the current study:

- 1. Criteria modified per amendment 1
- 1.1 Criterion modified per amendment 2
- 1.2 Male or female who participated in a Phase 1, 2 or 3 clinical study with Ad26.ZEBOV and/or MVA-BN-Filo and has been exposed to Ad26.ZEBOV and/or MVA-BN-Filo (or placebo) (Cohort 1);

or

Female who participated in a Phase 1, 2 or 3 clinical study with Ad26.ZEBOV and/or MVA-BN-Filo and became pregnant with estimated conception within 28 days after vaccination with MVA-BN-Filo (or placebo) or within 3 months after vaccination with Ad26.ZEBOV (or placebo) (Cohort 2);

or

Child born to a female subject exposed to Ad26.ZEBOV and/or MVA-BN-Filo (or placebo) in a Phase 1, 2, or 3 clinical study who became pregnant with estimated conception within 28 days after vaccination with MVA-BN-Filo (or placebo) or within 3 months after vaccination with Ad26.ZEBOV (or placebo) (Cohort 3).

Note: Each local authority will determine which cohorts will be opened for enrollment in their region. It is not mandatory to open all cohorts for enrollment. As a result, a local authority may restrict enrollment to 1 or 2 cohorts, rather than allowing enrollment in all cohorts.

2. Must sign an ICF for the current study (or their legally acceptable representative must sign) indicating that he or she understands the purpose of, and procedures required for, the study and is willing to participate in the study (or let their child participate).

Note: Assent is also required of children capable of understanding the nature of the study (typically 7 years of age and older) as described in Section 16.2.3.

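### Pregnancy incidence is analysed on roll-over enrollees although a window pregnancy is itself an entry route, so it can be biased in either direction

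*Protocol*

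**What the plan says.** Section 11.1 makes pregnancy conceived in the post-vaccination window an incidence endpoint: "Incidence of pregnancy with estimated conception within 28 days after vaccination with MVA-BN-Filo or within 3 months after vaccination with Ad26.ZEBOV". Section 11.5 summarises it by original randomization. The synopsis (Statistical Methods) promises incidence rates of pregnancy, overall and by outcome, with two-sided 95% confidence intervals.

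Section 11.3 fixes the population: "The study endpoints will be analyzed based on the Full Analysis set as the primary analysis population". That set is limited to subjects enrolled in the roll-over study who have at least one post-baseline visit. No exception is made for the pregnancy endpoints.

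Four rules decide which women are in it:

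- Section 5.1 admits to Cohort 2 only women who already conceived in the window.
- Any exposed subject may enter Cohort 1, which is the only route for a woman without a window pregnancy.
- Section 3.1 adds that "a local authority may restrict enrollment to 1 or 2 cohorts, rather than allowing enrollment in all cohorts".
- Everyone needs fresh consent: "Must sign an ICF for the current study (or their legally acceptable representative must sign".

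In the Time and Events Schedule, a pregnancy follow-up row appears only for Cohort 2, where it covers "Information on obstetric history, maternal/paternal risk factors, pregnancy outcome (including spontaneous/elective abortion, intrauterine death/stillbirth, information on delivery". The Cohort 1 table has no such row, although its footnote e copies relevant data from the original study.

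**The concern.** An incidence needs a denominator of women at risk who were gathered without regard to whether they had the event. Here the event is one of the entry criteria. Conception falls within 28 days or 3 months of a vaccination given in the original study, while consent to the roll-over is preferably taken at the last visit of that study. The event will therefore normally have happened before the woman is enrolled.

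Which women enter then depends on what each local authority opened and on who agreed to join. A region with Cohort 2 but not Cohort 1 supplies cases without their denominator. A region with Cohort 1 but not Cohort 2 supplies a denominator and may supply no cases. Even with both open, a difference in consent between women who did and did not conceive shifts the proportion.

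At stake is a descriptive safety rate that could be read as the frequency of pregnancy shortly after vaccination. A 95% interval computed on the enrolled women reflects sampling error only, not this selection.

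**Working it through.** **Inputs.** The protocol states no pregnancy rate, consent rate, number of vaccinated women or regional split, so there is no planned figure to reproduce. Everything below is assumed for illustration. Women only are considered, in regions where at least one of Cohorts 1 and 2 is open.

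- p: true proportion of vaccinated women with a window pregnancy; 0.5% to 5% assumed.
- a: share of women in regions with Cohort 2 open and Cohort 1 closed.
- b: share of women in regions with Cohort 1 open and Cohort 2 closed. Window-pregnant women there join Cohort 1, and their pregnancies are taken as not counted.
- cp, cn: consent rates of women with and without a window pregnancy.

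**Formula.** Cases are counted only where Cohort 2 is open. Women without a window pregnancy are enrolled only where Cohort 1 is open.

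Reported incidence = cp·p·(1 − b) / [cp·p + cn·(1 − p)·(1 − a)]

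**Results.** The middle column works the case p = 2%; the last gives reported over true incidence for p from 0.5% to 5%.

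| Scenario | p = 2% | Ratio |
|---|---|---|
| Both cohorts open everywhere, equal consent | 2.00% | 1.00 |
| a = 0.25, full consent | 0.02 / (0.02 + 0.98 × 0.75) = 0.02 / 0.755 = 2.65% | 1.31 to 1.33 |
| a = 0.50, full consent | 0.02 / (0.02 + 0.98 × 0.50) = 0.02 / 0.51 = 3.92% | 1.91 to 1.99 |
| b = 0.25, full consent | 0.02 × 0.75 = 1.50% | 0.75 |
| b = 0.50, full consent | 0.02 × 0.50 = 1.00% | 0.50 |
| a = b = 0.25, full consent | 0.015 / 0.755 = 1.99% | 0.98 to 1.00 |
| Both open, cp = 0.9, cn = 0.6 | 0.018 / (0.018 + 0.588) = 0.018 / 0.606 = 2.97% | 1.46 to 1.50 |
| Both open, cp = 0.6, cn = 0.9 | 0.012 / (0.012 + 0.882) = 0.012 / 0.894 = 1.34% | 0.67 to 0.68 |

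**What follows.** The regional and consent mechanisms each act in either direction, and some mixes nearly cancel. Choosing a narrower denominator among enrolled women, or restricting by region, can remove the regional part. It cannot remove the consent part, because the women who declined are outside the set. If both numerator and denominator come from all women vaccinated in the original studies, the estimate does not depend on a, b, cp or cn.

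**The case against.** **The analysis plan will define the denominator.** Section 11 leaves details to it, and no section says that Cohorts 1 and 2 are pooled across regions into one proportion. A plan could restrict by region or cohort within 11.3 and remove the regional part. That stands. It could not count women outside the enrolled set without departing from 11.3, so selection by consent would remain.

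**The downward regional case is not established.** A reader might infer from the missing pregnancy row for Cohort 1 that pregnancies are lost wherever Cohort 2 is closed. The documents do not show this. A woman with a window pregnancy also qualifies for Cohort 1, footnote e of that table copies relevant original-study data, and 9.1 lists pregnancy follow-up among items that may be captured from the original data set. The qualifier in 9.1, that items must be available and applicable to the cohort, leaves the matter open. The ratios 0.75 and 0.50 hold only if those pregnancies are not carried over.

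**Cohort 2 without Cohort 1 may be rare.** The design moves women from Cohort 2 into Cohort 1 after the pregnancy, which fits poorly with Cohort 1 being closed. Section 3.1 nevertheless permits it, and nothing shows how often it occurs.

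**The consequence is limited.** The study is descriptive, without hypotheses or tests. Pregnancy incidence is an endpoint but not a stated objective. The interval for it is promised only in the synopsis, since 11.5 attaches intervals to serious adverse events. Section 11.2 also warns of observational bias, loss to follow-up and uncollected data. These points limit the weight of the concern, but 11.2 does not mention entry through the outcome, and a descriptive rate still needs an interpretable denominator.

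**Conclusion.** The concern holds as a possible bias, not a demonstrated one. The analysis set in 11.3 is partly selected on the outcome that the pregnancy incidence is meant to measure, and a plan that stays within 11.3 cannot fully repair this.

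A reader might go further and infer that the incidence is certainly biased, or biased in a known direction. The documents do not support that: no section says which cohorts any region opened or how consent relates to pregnancy, and the bias is zero when both cohorts are open everywhere and consent is unrelated to pregnancy. Nor is the range of 0.50 to 1.99 an estimate of the error. It shows what assumed regional shares of 25% or 50% and consent splits of 90% against 60% would do.

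Pregnancy outcomes and live births are not exposed to the denominator problem if given as proportions of followed window pregnancies, though they stay conditional on consent. Because 11.1 and 11.5 call these incidence as well, the wording should be settled for them too. This should be corrected; it does not threaten the serious adverse event objectives.

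**What to change.** In 11.3 and 11.5, exempt pregnancy incidence from the Full Analysis set. Take both parts from original-study data, by original randomization: as numerator, the window pregnancies that 12.3.2 says must already have been reported to the sponsor; as denominator, all women vaccinated in the contributing studies, with exposure as defined in 9.2.1. Do this where the original-study consents allow. Those consents are not shown, and 9.1 and 16.2.3 require a signed form before data collection in this study.

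Where they do not allow it, limit the incidence to regions with Cohorts 1 and 2 both open, and label it conditional on enrolment and consent. This removes the regional part but not the consent part.

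Report pregnancy outcomes and live births as proportions of followed window pregnancies, with the number of unknown outcomes shown.

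The cost is about a sentence in each of the two sections and some linkage to original-study data. The downside is that some counted pregnancies will have no known outcome.
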